Nortriptyline is a tricyclic antidepressant (TCA) widely used in the treatment of neuropathic pain conditions, including diabetic neuropathy and postherpetic neuralgia. It exerts its analgesic effects primarily through inhibition of norepinephrine reuptake, with modest serotonergic reuptake inhibition, enhancing descending inhibitory pain pathways in the central nervous system. Nortriptyline also interacts with muscarinic, histaminergic, and  $\alpha$ 1-adrenergic receptors, contributing to both therapeutic and adverse effects. Clinical studies have shown nortriptyline to be effective in improving pain scores in chronic neuropathic pain and it is included in multiple international guidelines as a first-line treatment. Common side effects include dry mouth, dizziness, constipation, and sedation, which may limit dose escalation in some patients.

PainCart® and NeuroCart® are two comprehensive and validated test batteries commonly used in early-phase drug studies to profile pharmacodynamic effects of (novel) drugs. PainCart® consists of an evoked pain test battery that was used previously to amongst others profile morphine, pregabalin and the opioid fentanyl.¹¹ NeuroCart® is a CNS test battery that is used to assess drug-induced changes in CNS functioning. The batteries have previously been used together to evaluate possible synergistic effects of two analgesics, and to determine the CNS and analgesic profile of a novel investigational drug.¹¹¹

The aim of this first human experimental pain study, the QSPainRelief-novel-B-trial, is to investigate the analgesic effects and effects on CNS functioning of morphine and nortriptyline as an analgesic combination in patients with chronic neuropathic pains, compared to each of the two analgesics alone and to placebo.

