#### **Objectives**

The primary objectives are:

[figure not shown]
 To evaluate the analgesic effects of morphine, nortriptyline and the two drugs as combination using PainCart®

The secondary objectives are:

- To evaluate the effects on central nervous system (CNS) functioning of morphine, nortriptyline and the two drugs as combination as measured using NeuroCart®
- To compare the tolerability of morphine alone, nortriptyline alone and the two drugs when given together
- To evaluate the blood pharmacokinetics of morphine, nortriptyline and the two drugs as combination

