The measurement techniques performed in this study (PainCart® and CNS tests) are considered to be safe and with minimal risk. Capsaicin application on the volar forearm may cause some transient skin irritation on the application site. The skin may become red and/or more sensitive to e.g., warm water, and to touch (a slight burning sensation). After one or two days the effects will generally resolve.

**Table 1.** Visit and Assessment Schedule

	SCR		Treatment period 1 - 4 								FU 						
	SCR	Day -1						С	Day 1							Day 2	
Time point Assessment	Up to -42 d to -5 days	Day -1	Pre- dose	0 h	1h	2 h	3 h	3.5 h	4 h	5 h	6 h	6.5 h	7.5 h	8 h	9 h	24 h	+14 d ± 2 d
Informed consent	Х																
Demography	х																
Inclusion and exclusion criteria	х		х														
Medical history	х																
Height, Weight³, BMI	х																Х
Admission to clinic		Х															
Physical examination 	х		X 														Х
Virology	х																
BsHaem, BsChem, BsGluc, Urinalysis	х	х															Х
UrDrug, BrAlc, UrPreg 	х	Х															Х
Temperature	х	Х	Х													Х	Х
ECG	х		Х											х		х	Х
General symptoms	х		Х		х	х				х				х		х	
Vital Signs (Pulse Rate, BP, RR, O 2 saturation) 			х							х		Х		х		х	Х
Meals / snack 			X8		х				х					х	х	х	
Drug (-placebo) administration				х		х				х							
PK sample			Х		х	X 9			х	X 9	х			х		х	
Capsaicin application	X 		X 														
Capsaicin task – Von Frey test 			х		х		х		Х		х		Х		Х		
PainCart®12,13	X 		X 		Х		Х		Х		Х		Х		Х		
NeuroCart®12	X 		X 		х	х		х		х		Х			х		
pEEG			X 			Х				Х		Х			Х		

VVLT 	х					х			Х					
STAI	х		х		х	х		Х	Х	Х		Х		
BSI		Х										Х		
Discharge	Х												X 	
(S)AE			continuous						Х					
Concomitant medication	Х		continuous						Х					

BP = Blood Pressure, HR = Heart Rate, RR = Respiratory Rate, SCR = Screening, EEG = Electroencephalogram, PK = Pharmacokinetics, AE = Adverse Event, (S)AE = Serious Adverse Event, UrDrug = Urine Drug Screen, UrPreg = Urine Pregnancy test, BsHaem = Blood Sample Haematology, BsChem = Blood Sample Chemistry, BsGluc = Blood Sample Glucose, BsBiomarker = Blood Sample Biomarker, BrAlc = Breath Alcohol Test., BMI = Body Mass Index

- At least 7 days between treatment periods

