#### 2.2.2 Clinical information

#### Clinical pharmacology

#### Nortriptyline

Nortriptyline is a tricyclic antidepressant (TCA) that is widely used in the treatment of neuropathic pain. Its analgesic effects are primarily mediated through potent inhibition of norepinephrine reuptake and modest inhibition of serotonin reuptake, which enhances descending inhibitory pain pathways in the spinal cord and brain. Nortriptyline also acts as an antagonist at muscarinic cholinergic, histamine H1, and alpha-1 adrenergic receptors, contributing to both its therapeutic effects and side effects profile. Although nortriptyline does not bind directly to opioid receptors, preclinical and clinical studies support its use in combination with opioids like morphine, potentially offering additive or synergistic analgesia. Its pharmacokinetics involve extensive hepatic metabolism, primarily by CYP2D6, with a typical elimination half-life of 18–44 hours, supporting once-daily dosing.

In addition to its reuptake inhibition, nortriptyline antagonizes muscarinic cholinergic, histamine H1, and alpha-1 adrenergic receptors, which contributes to both its analgesic efficacy and side effect profile, including sedation and anticholinergic effects. It does not act on opioid receptors and does not have known activity at the sigma-1 receptor.

Nortriptyline is rapidly absorbed after oral administration and undergoes extensive first-pass hepatic metabolism, primarily via cytochrome P450 2D6 (CYP2D6).25b The absolute bioavailability is approximately 45-60%, with peak plasma concentrations occurring within 2 to 8 hours.

The exact mechanisms by which nortriptyline exerts its analgesic effects are not yet fully understood. However, its ability to modulate serotonin and other neurotransmitters involved in pain processing suggest a multifaceted approach to pain relief.

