#### Morphine

Morphine and M6G notably contribute to the analgesic effect after administration of morphine, which is rapidly metabolized in the liver.26 As the study aims to have a better understanding of the analgesic effects of morphine and M6G in patients with chronic neuropathic pains and generate data that may be used for PK-PD modelling, an IV dose is deemed preferable over an oral dose.

Both morphine HCl 3 mg and 7 mg will be administered as intravenous bolus injection in 1 minute. In both the treatment arm with nortriptyline + morphine, and treatment arm with placebo + morphine, the bolus injections will be administered at t = 2 h (3 mg) and t = 5 h (7 mg).

The 3 mg and 7 mg doses of morphine are equianalgesic to minimally therapeutic and clearly therapeutic doses of buprenorphine as observed in a previous study where potentiation of buprenorphine and milnacipran was assessed.  Buprenorphine is 30-40 times more potent than IV morphine.  Testing two morphine doses, one minimally therapeutic and one clearly therapeutic, on a single study day will allow for detailed exploration of possible synergistic/potentiating effects of the combination treatment during the PKPD analysis. Furthermore, the 3 mg and 7 mg morphine doses are based on a calculation using pre-existing and published morphine and pregabalin  PK/PD models. Refer to Figure 1 for the predictions of effect of these doses on PTT for the cold pressor test. As illustrated in Figure 1, the proposed doses are predicted to yield an increased analgesic effect, while expected to have manageable side effects.

**Figure 1.** Predicted effect on cold pressor PTT based on the integrated PKPD model of morphine and pregabalin. Black line is the predicted placebo response, red line the proposed morphine dose of 3mg IV at t = 2 h and 7mg IV at t = 5 h, the green line the single oral dose of pregabalin 300mg at t = 0 and blue line the combination treatment of above-mentioned doses and drugs.

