## morphine + nortriptyline versus morphine

All the collected PD endpoint will be analysed with descriptive statistics. However, only PD endpoints collected after start of the first IV bolus injection will be used for the mixed model ANCOVA analysis.

Final analysis of specific PD endpoints (PainCart® and CNS tests) will be performed in sequence to limit the number of tests. Refer to Table 3 and 4 below. Initially, only the parameters listed in the 'first round analysis' column will be analysed following methods described further along this paragraph.

Only in case one or more of the endpoints listed in the 'first round analysis' column reaches statistical significance in any of the contrasts, the endpoints mentioned in the 'second round analysis' will be analysed. Whether to proceed with the 'second round analysis' is evaluated separately for each test.

Due to the large amount endpoints obtained from pEEG, those results will be analysed separately to allow for comprehensive evaluation of all power bands, EEG-derivations taken together.

BSI endpoints will be presented in a frequency table.

**Table 9.** PainCart® endpoints

PainCart® endpoints			
Test	First round analysis	Second round analysis	
Pain pressure	PDT, PTT	AUC, VAS, McGill	
Heat Pain	PDT	VAS, McGill	
Cold pressor	PDT, PTT	AAC, VAS, McGill	
Electrical stair	PDT, PTT	AUC, VAS, McGill	
Electrical Burst	PDT, PTT	AUC, VAS, McGill	
CPM PDT		NA	

**Table 10.** CNS test endpoints

CNS test endpoints			
Test	First round analysis	Second round analysis	
Adaptive tracker	Average performance	NA	
Body sway	Antero-posterior sway	NA	
VAS B&L	Alertness	Mood; calmness	
VAS Bowdle	Feeling High	- Internal perception	
		- External perception	
N-back	- Average reaction time (ms) (two-	- Average reaction time (ms) (zero- and	
	back)	one-back)	
	- Number of correct targets (two-	- Number of correct targets (zero- and	
	back)	one-back)	
	- Number of incorrect targets (two-	- Number of incorrect targets (zero- and	
	back)	one-back)	
	- Number of faulty non-target	- Number of faulty non-target responses	
	responses (two-back)	(zero- and one-back)	
VVLT	- Delayed recall (number correct)	- Immediate recall trial 3 (number	
		correct)	
		- Delayed recognition (number correct)	
		- Delayed recognition (reaction time)	
Eye Movement	- Saccadic peak velocity	NA	
	(degrees/sec)		
	- Saccadic reaction time (sec)		
	- Saccadic Inaccuracy (%)		
	- Smooth pursuit (%)		
Pupillometry	- Pupil/iris ration (left and right)	NA	

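### The 1 h round, the only post-dose PainCart round before study morphine, gets descriptive statistics only, so the nortriptyline part of the objective has no model-based difference or confidence interval

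*Protocol*

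**What the plan says.** The synopsis gives the primary objective as "To evaluate the analgesic effects of morphine, nortriptyline and the two drugs as combination using PainCart". A secondary objective is worded in the same way for NeuroCart. The Rationale, repeated in section 2.2.1, sets the aim of studying the combination "compared to each of the two analgesics alone and to placebo". (Table 2 names fluvoxamine where the synopsis names nortriptyline.)

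Both treatments start with an oral dose at 0 h, nortriptyline in one and placebo in the other. Section 2.7.1 then gives the same two morphine boluses in both, at 2 h and 5 h. Table 1 schedules PainCart after dosing at 1, 3, 4, 6, 7.5 and 9 h, with Von Frey and NeuroCart rounds also at 1 h.

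Section 2.13.6 lists a single contrast, "morphine + nortriptyline versus morphine". It then states: "All the collected PD endpoint will be analysed with descriptive statistics". The next sentence limits the model: "only PD endpoints collected after start of the first IV bolus injection will be used for the mixed model ANCOVA analysis". The descriptive statistics are n, mean, SD, SEM, median, minimum and maximum by treatment and time, with listings by subject and individual graphs.

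**The concern.** At 1 h the two regimens differ only in nortriptyline versus placebo, within the same subjects and under the blind. No other post-dose PainCart round has that property. The plan describes these data but does not estimate from them: there is no paired difference, baseline adjustment, period term or confidence interval. A by-treatment mean with its SD does not use the crossover pairing.

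Two things are at stake. The objective and aim ask about nortriptyline itself, and the model answers only what nortriptyline adds to morphine. In addition, a difference seen after the bolus cannot be read beside a model-based estimate of any nortriptyline effect already present before morphine.

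**Working it through.** **Which rounds enter the model.** PainCart rounds after dosing: 1, 3, 4, 6, 7.5 and 9 h. First bolus: 2 h. One round falls before study morphine and five after. Section 2.13.5 divides the residual variance by five post-dose measurements, which matches the five rounds that remain. Leaving 1 h out therefore costs the combination contrast nothing.

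**Reproducing the plan's own figures.** Table 6 obtains its cross-over CV from Table 5 as sqrt(exp(2 × (trt*subject + residual/5)) − 1). For CHDR1311 part 1 this is sqrt(exp(2 × (0.02615 + 0.04216/5)) − 1) = 26.8%, against 26.7% stated. The other three give 28.0%, 23.5% and 19.0%, against 28.0%, 23.5% and 18.9%. Table 6 reproduces to 0.1 percentage point. Table 8 is not used: at CV 30% and N = 24, a two-sided paired calculation with the CV read as within-subject gives 71.3%, against 82.5% stated.

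**Precision of a 1 h contrast.** Only one round contributes, so the residual is not divided by five:

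- SD of the log difference = sqrt(2 × (trt*subject + residual))
- SE = SD / sqrt(24); 95% half-width = 2.074 × SE (t, 22 df)

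| Source study | SD | SE | Half-width (log) | CI factor |
|---|---|---|---|---|
| CHDR1311 part 1 | sqrt(2 × 0.06831) = 0.370 | 0.0754 | 0.156 | 1.17 |
| CHDR1311 part 2 | sqrt(2 × 0.07068) = 0.376 | 0.0767 | 0.159 | 1.17 |
| CHDR1425 | sqrt(2 × 0.04633) = 0.304 | 0.0621 | 0.129 | 1.14 |
| CHDR1431 | sqrt(2 × 0.03439) = 0.262 | 0.0535 | 0.111 | 1.12 |

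The planned five-round contrast has factors of 1.08 to 1.12. With 20 completers the 1 h factors become 1.13 to 1.19.

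**Illustrative power.** For a ratio of 1.25 (log 0.223), noncentral t with 22 df gives 81%, 79%, 93% and 98%. That ratio is the planning effect for pregabalin versus placebo. The protocol gives no nortriptyline effect at 1 h, so these values only show scale.

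**How early 1 h is.** Section 2.2.2 describes absorption "with peak plasma concentrations occurring within 2 to 8 hours" and a half-life of 18 to 44 h. Assuming one-compartment first-order absorption with no lag, the 1 h concentration is 34% to 94% of the peak. With an assumed lag of 1 h it would be 0%. The protocol plans to report a lag time but gives no value.

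**Carry-over.** Seven days is 168 h. At a 44 h half-life, 168/44 = 3.8 half-lives and about 7% remains. At 18 h, 168/18 = 9.3 half-lives and about 0.2% remains.

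**The case against.** The strongest reply is that the quoted rule is correct. A round before morphine would dilute a contrast that concerns morphine with and without nortriptyline, and five rounds remain as the sample-size section assumes. That stands, and the rule should stay for that contrast.

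A reader might infer that the 1 h data are thrown away and that nortriptyline gets no estimate of any kind. The documents do not support this. The data stay in the listings, graphs and descriptive tables, so the 1 h means for both treatments will be seen. What is missing is a modelled difference with its interval.

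A reader might also infer that a 1 h contrast would fulfil the nortriptyline objective. It would not. The round precedes the stated peak, and exposure is still changing between 1 h and the later rounds, so it is not a like-for-like reference for them either.

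Three further objections limit the contrast without defeating it:

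- **Timing.** NeuroCart takes about 40 minutes and runs before PainCart when both fall at the same time point, and cold pressor comes late in the PainCart order. The protocol does not establish that every 1 h test ends before the 2 h bolus. The order of the 2 h NeuroCart and pEEG relative to the bolus is also not stated.
- **Background opioids.** The round is free of study morphine only. Inclusion criterion 2 requires current opioid-type treatment, while exclusion criterion 6 bars medication in the preceding 14 days. These passages must be reconciled.
- **Gating.** Second-round analyses open on significance in any contrast, and there is no multiplicity adjustment. An added contrast would widen that gate unless it is excluded.

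The study is declared exploratory and allows further exploratory analyses, but it does not commit to this one.

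**Conclusion.** The point holds in a limited form. The post-bolus restriction is right for the combination contrast. The gap is that no separate contrast uses the one PainCart round that compares nortriptyline with placebo before study morphine, while the objective and aim claim to address nortriptyline alone.

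On cold pressor PTT, such a contrast would carry a 95% CI factor of 1.12 to 1.17 with 24 subjects. This assumes that the Table 5 variance components apply to these patients, that all 24 complete both periods, and that the test is finished before the bolus. It is usable precision for an early estimate. It does not show that an effect exists at 1 h or would be detected, so the 79% to 98% power at a ratio of 1.25 should not be quoted as the power of this trial for nortriptyline.

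**What to change.** In section 2.13.6, leave the post-bolus contrast unchanged and add a separate exploratory 1 h contrast of nortriptyline versus placebo. Fit treatment and period as fixed effects, subject as random and baseline as covariate, and report the estimate with its 95% CI. State four conditions:

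- only assessments actually recorded before the first bolus are used;
- the result does not count toward opening the second-round analysis;
- 1 h is an early, pre-peak time point, at which a null result is not evidence of no effect;
- placebo data in period 2 may carry residual nortriptyline.

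Also narrow the objective and aim to the add-on effect of nortriptyline on morphine plus this early estimate, and drop the claim of a full comparison with nortriptyline alone.

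No new data are needed. The cost is a short addition to 2.13.6, an edit to the objective and aim, and a few more exploratory estimates of limited sensitivity. Restricting the contrast to first-round endpoints measured at 1 h would keep their number small. Von Frey is not in Table 9, so it would have to be named separately if wanted.

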#### **Trial Design**

This is a randomized, double-blind, double dummy, placebo-controlled, two-way cross-over study to investigate the pharmacodynamic effects and adverse effects of morphine and nortriptyline in patients with chronic neuropathic pains.

Each study participant will receive the following study treatments:

- Morphine 3 mg IV + 7 mg IV + placebo
- Nortriptyline 75 mg orally + Morphine 3 mg IV + Morphine 7 mg IV

Protocol time Treatments	0h00m	2h00m	5h00m			
1	Placebo	Morphine 3 mg IV	Morphine 7 mg IV			
2	Nortriptyline 75mg	Morphine 3 mg IV	Morphine 7 mg IV			

In total, each subject will be exposed to two treatment options. Each treatment period will consist of one study visit to the clinical research unit. During this visit, arrival to the clinical research unit will be in afternoon of day before dosing (Day-1). In the morning of the next day (Day 1), subjects will receive the study treatment prior which and after which pharmacokinetic (PK) assessments and the pharmacodynamics (PD) will be performed. Subjects will be discharged in the afternoon of Day 2. Each study period will be followed by a wash-out period of at least 7 days and a final follow-up visit 7-14 days after the last dosing day.

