## Ethical Considerations relating to the Clinical Trial including the expected Benefit to the individual Subject or Group of Patients represented by the Trial Subjects as well as the Nature and Extent of Burden and Risks

This study will provide more insight in a combination treatment for patients suffering from chronic pain and determine if the addition of nortriptyline is better than morphine alone. Morphine and nortriptyline are registered drugs which are widely used in the clinic, amongst other analgesics. The safety profiles of these compounds are well known. Both analgesic and adverse effects are likely to occur. Symptoms such as sedation, somnolence, dizziness, fatigue, reduced vigilance, are to be expected following administration for both compounds, but will be closely monitored by medically trained staff as part of the study objectives.

This study will produce novel information on the clinical utility of morphine and nortriptyline when coadministered, i.e., potentiation of analgesic effects (profiled using PainCart®) and characterization of side effect profile (using CNS biomarkers and NeuroCart®).

Study subjects will undergo a medical screening and eligibility will be checked multiple times before administering the study drug. During the clinical study, administration will be done in the clinic under medical supervision. Subjects will be closely monitored and will be discharged by a physician from the unit only if their medical condition allows. In case of nausea and/or vomiting anti emetic, treatments will be administered with metoclopramide 10 mg intravenously as a single dose, which can be repeated if nausea or vomiting persists.

At doses above 3 mg, morphine may decrease respiration in dose-dependent manner. While the dose of 7mg be administered are expected to be manageable. The total maximum dose of morphine IV on a single day is expected to provide adequate analgesic properties and measurable effects on neurocognitive tests, while having manageable adverse effects. As an additional safety measure, oxygen saturation will be measured after the first morphine administration at fixed timepoints as indicated in the Schedule of Assessments, and additionally when deemed necessary.

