#### **2.4 OBJECTIVES AND ENDPOINTS**

**Table 2.** Objectives and Endpoints

Objectives	Endpoints				
Primary					
To evaluate the analgesic effects of morphine, fluvoxamine and the two	
 
Pressure Pain: Pain Detection Threshold (PDT), Pain Tolerance Threshold (PTT), Area Under the Curve (AUC), post-test Visual Analogue Scale (VAS)
 
				
drugs as combination using PainCart	
 
Heat pain (pre-cold pressor: unexposed/normal and capsaicin-exposed skin) (only for eligible subjects): PDT, and post-test VAS
 
				
	

Cold Pressor: PDT, PTT, Area Above the Curve (AAC), post-test VAS

				
	4. Electrical Stair test: PDT, PTT, AUC, post-test VAS				
	5. Electrical burst test: PDT, PTT, AUC, post-test VAS				
	

Conditioned Pain Modulation (CPM) Response (change from heat pain pre- and post-cold pressor): PDT

				
	
 
Short Form McGill Pain Questionnaire (SFMPQ) for pressure pain, heat pain, cold pressor, electrical stair test and electrical burst test
 
				
Secondary					

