#### 2.5.2 Number of patients

A total of 24 subjects is planned to be enrolled. All subjects will participate in four study occasions.

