Using that data, a sample size calculation was performed. The sample required to achieve a power of at least 80% to detect an expected difference on the cold pressor task (PTT) of 5 seconds (25% of an average score, based on 4 studies, under placebo of 20 seconds) at a two-sided significance level of 0.05, are given in the following Table (Table 6) for a range of within subject CV values:

**Table 8.** Sample size

Within subject CV	Actual power	Sample size
20%	0.796	20
25%	0.845	24
30%	0.825	24

Assuming a within subject CV of 30%, a sample size of 24 would yield a power of over 80% (82.5%) and thus suffices, for the contrast pregabalin - placebo.

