#### *Inferential methods*

The study is exploratory, and no formal null hypothesis is set. No adjustments for multiple comparisons will be applied.

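### Fourteen primary pain endpoints and 13 secondary CNS endpoints get a model-based treatment difference and 95% CI only if another endpoint of the same test is significant

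*Protocol*

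**What the plan says.** Section 2.4, Table 2, lists the primary pain endpoints without ranking them. The first entry reads "Pressure Pain: Pain Detection Threshold (PDT), Pain Tolerance Threshold (PTT), Area Under the Curve (AUC), post-test Visual Analogue Scale (VAS". The cold pressor, electrical stair and electrical burst tests follow the same pattern (AAC replaces AUC for cold pressor). Heat pain has PDT and VAS, CPM has PDT, and McGill is listed for five tests.

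Section 2.13.6 splits these endpoints in Tables 9 and 10. First-round endpoints are always modelled. Second-round endpoints are modelled "Only in case one or more of the endpoints listed in the 'first round analysis' column reaches statistical significance in any of the contrasts", judged test by test, and only one contrast is listed (morphine + nortriptyline versus morphine). The stated purpose is to limit the number of tests. All endpoints receive descriptive statistics. The estimated difference, 95% CI, least squares means and p-value come from the mixed model.

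Section 2.13.5 calls the study exploratory with no formal null hypothesis, and adds: "No adjustments for multiple comparisons will be applied". The Synopsis gives as one aim the "characterization of side effect profile (using CNS biomarkers and NeuroCart" battery.

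**The concern.** An endpoint declared in Table 2 should get a treatment estimate whatever the p-value of a neighbouring endpoint. Under section 2.13.6 it may not. McGill and post-test VAS for a pain test depend on PDT or PTT. Mood and calmness depend on alertness, internal and external perception on feeling high, immediate recall and recognition on delayed recall, and zero- and one-back on two-back.

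Two things are at stake. First, a test whose first-round endpoints are not significant leaves its other declared endpoints with means and SDs by treatment and time only. Those do not show how large an effect the data exclude, which is what a side-effect profile needs. Second, second-round estimates appear only after a significant correlated result, so on average they overstate the effect.

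**Working it through.** **1. Counts (heat pain counted once).**
- Table 9, first round: pressure 2 + heat 1 + cold 2 + stair 2 + burst 2 + CPM 1 = 10.
- Table 9, second round: 3 + 2 + 3 + 3 + 3 = 14. The total of 24 equals the Table 2 list (4 + 2 + 4 + 4 + 4 + 1, plus 5 McGill).
- Table 10, second round: Bond & Lader 2 + Bowdle 2 + N-back 4 × 2 = 8 + VVLT 3 = 15. The two N-back incorrect-target measures are not in Table 2, so 13 are declared secondary endpoints.
- The 29 second-round measures by number of first-round endpoints in their test: one endpoint, 9 measures (heat 2, Bond & Lader 2, Bowdle 2, VVLT 3); two endpoints, 12 (pressure, cold, stair, burst); four endpoints, 8 (N-back).

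**2. The plan's own power figure.** Inputs: "A total of 24 subjects is planned to be enrolled", "In total, each subject will be exposed to two treatment options", an "expected difference on the cold pressor task (PTT) of 5 seconds" on a placebo mean of 20 s, within-subject CV 30%, "at a two-sided significance level of 0.05". SD of the paired difference = √2 × 0.30 × 20 = 8.49 s; 5/8.49 = 0.589; Φ(0.589 × √24 − 1.96) = 0.823, against the stated 0.825. This is for a pregabalin – placebo contrast on one endpoint, so it does not show how often the first-round conditions of this trial would be met.

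**3. How often a test fails the condition.** The mixed-model contrast is approximated by a paired t-test, n = 24, two-sided 0.05. The effect size and the correlations are assumptions; the protocol gives neither. With 0.5 SD of the paired difference, one endpoint has power 0.65 (noncentral t, 22 or 23 df), a miss rate of 35%. This rises to 39% with 22 completers and 44% with 20. With that effect on every first-round endpoint, simulation of 40,000 trials gives:

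| First-round endpoints in the test | Correlation | Condition fails |
|---|---|---|
| 1 | – | 35% |
| 2 | 0 to 0.9 | 12–28% |
| 4 | 0 to 0.9 | about 1–23% |
| All five pain tests together (9 endpoints) | 0 to 0.7 | about 0–9% |

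If only one of PDT and PTT carries the 0.5 SD effect, the two-endpoint figure is about 33%.

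**4. Using the protocol's variances (cold pressor PTT only).** From Table 5, SD of the log difference = √(2 × (trt*subject + residual/5)) = 0.263, 0.275, 0.232 and 0.188 for the four studies. With 22 df:
- Ratio 1.25 (the planned 25%): ln 1.25 = 0.223; missed in 2.2%, 3.3%, 0.6% and under 0.1%.
- Ratio 1.07 (smallest in Table 7): ln 1.07 = 0.068; missed in 77%, 79%, 72% and 61%.

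These are miss rates for PTT alone; a significant PDT would also admit the second round.

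**5. Selection of reported estimates.** With a true effect of 0.30 SD on first- and second-round endpoints and correlation 0.6 (both assumed), the mean second-round estimate among trials meeting the condition is 0.44 with one first-round endpoint and about 0.42 with two. That is an overstatement of 0.14/0.30 = 47% and 0.12/0.30 = 40%.

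**6. What the rule buys.** With no effect on any endpoint of a test (correlation 0 to 0.7), the chance of at least one false positive in that test is:
- one first-round endpoint of three: 5% with the rule, 11–14% without;
- two first-round endpoints of five: 8–10% with the rule, 15–23% without.

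**The case against.** The best defence is that this is a prespecified ordering of tests in an exploratory study. It limits the number of tests as stated, and step 6 shows that it roughly halves the false-positive rate within a wholly unaffected test. Every endpoint still gets means, SDs and graphs, and further exploratory analyses are permitted. Much of the CNS battery is modelled unconditionally (adaptive tracking, body sway, eye movements, pupillometry, SRT, STAI), and adverse events are summarised separately.

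All of that stands, and it rules out several stronger readings:
- A reader might take 35% as the failure rate of the rule in general. It applies to 9 of 29 measures, at an assumed effect. Tests with two or four first-round endpoints fail less often.
- A reader might expect all 14 primary measures to go unestimated together. Under the same assumptions this is rare (about 0–9%).
- A reader might infer that the protocol treats non-significance as proof of no effect. It does not say so; its stated reason is fewer tests.
- A reader might infer that the rule controls no error at all. It gives weak control within a test.

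The defence does not explain why estimates and CIs must be withheld in order to limit tests. Optional later analyses are a poor substitute for prespecified ones, because they would be chosen after the data are seen.

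**Conclusion.** The concern holds as a mismatch between section 2.4 and section 2.13.6. Fourteen declared primary pain endpoints and 13 declared secondary CNS endpoints receive an adjusted difference and 95% CI only if another endpoint of the same test is significant. Both counts follow directly from Tables 2, 9 and 10. How often this matters depends on effects the protocol does not give. At an assumed 0.5 SD it ranges from about 1% to 35% per test, by number and correlation of first-round endpoints. On the protocol's own cold pressor variances, PTT would seldom miss the planned 25% effect (at most about 3%) but would usually miss a ratio of 1.07 (61–79%). The overstatement of 40–47% likewise rests on an assumed 0.30 SD effect and correlation 0.6. This is a reporting weakness that is cheap to remove; it does not undermine the design.

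**What to change.** In section 2.13.6, replace the two-round rule with wording such as:

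*The mixed model is fitted to every endpoint in the first- and second-round columns of Tables 9 and 10, and the estimated difference (morphine + nortriptyline minus morphine) with its 95% CI is reported for each, whatever the first-round result. P-values are reported for first-round endpoints only; second-round results are labelled as estimation. BSI (frequency table) and pEEG (separate analysis) are handled as already stated.*

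Referring to Tables 9 and 10 rather than Table 2 keeps in the measures that Table 2 omits, and the last sentence avoids a clash with the existing handling of BSI and pEEG. The sentence in 2.13.6 that points to Tables 3 and 4 should point to Tables 9 and 10.

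The cost is about 29 more fits (14 + 15) of a model already specified and a longer results table. It needs no new data, visits or patients. Keeping p-values to the first round preserves the aim of limiting the number of tests.
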